6.7. Baseline and Other Summaries and Analyses

6.7.1. Baseline Summaries

Analyses of baseline data will be based on the Safety Analysis Set.

6.7.1.1. Demographic Characteristics

The following demographic and baseline characteristics will be summarized by number and percentage:

- Gender (male, female);
- Age:
 - 18 to <65; 65 to <75; ≥75;
 - <65 vs ≥65;
 - <75 vs ≥75;
- Race (White, Black or African American, Asian, American Indian or Alaska Native, Native Hawaiian or other Pacific Islander, Not Reported, Unknown);
- Ethnicity (Hispanic, Not Hispanic, Not reported);
- Geographic Region (North America, Europe, Asia).

Age (continuous), height (cm), weight (kg), BMI (kg/m²) will be summarized with descriptive statistics (mean, median, standard deviation, minimum, and maximum).

6.7.1.2. Medical History

Medical history will be coded using the most current version of MedDRA and summarized by MedDRA's SOC and PT from the 'Medical History' CRF page. Each participant will be counted only once within each PT or SOC. Summaries will be ordered by SOC and PT (by alphabetical order for SOC and by descending order of frequency for PT in Part 1 and Part 2 combined). In case of equal frequency, alphabetical order will be used. Separate summaries will be provided for past and present conditions.

6.7.1.3. Disease Characteristics

The following baseline disease characteristics are collected under the "Pre-specified Primary Diagnosis" eCRF page and will be summarized by number and percentage:

- Current disease stage by Revised Multiple Myeloma International Staging System (R-ISS) - Stage I, II, and III, or unknown;
- Eastern Cooperative Oncology Group (ECOG) Performance status (ie, 0, 1);
- Cytogenetics (standard risk vs high risk);

- Presence of extramedullary disease;
- Baseline bone marrow plasma cells (<50% vs ≥50%);
- Type of myeloma (IgG vs non-IgG [IgA, IgD, IgE, IgM] vs light chain only [kappa light chain, lambda light chain]);
- Type of measurable disease at baseline (see [Section 5.2.9](#)):
 - Serum M-protein;
 - Urine M-protein;
 - Serum free light chain;
- Renal function (CrCl ≤60 mL/min vs >60 mL/min);
- Liver function normal (AST and total bilirubin ≤ ULN) vs impaired (AST or total bilirubin > ULN).

The following baseline disease characteristics will be summarized by descriptive statistics (mean, median, standard deviation, minimum, and maximum):

- Time since first diagnosis (months), defined as (date of first dose of study intervention – date of first diagnosis) / 30.4375;
- Time since onset of current episode, defined as (date of first dose of study intervention – date of onset of current episode) / 30.4375, where date of onset of current episode is the date of the last relapse.

6.7.1.4. Prior Anticancer Therapy

The prior anticancer therapies are collected under the ‘Response to Regimen -Prior Cancer Therapy’, ‘Non-drug Treatments – Prior Radiation Therapy’ and ‘Transplant Details - Prior’ eCRF pages.

The number and percentage of participants in each of the following anticancer therapy categories will be tabulated:

- Participants with prior IMiDs and type (eg, lenalidomide, pomalidomide, or thalidomide);
- Participants with prior PI and type (eg, bortezomib, cafilzomib, ixazomib);
- Participants with prior anti-CD38 antibody and type (eg, daratumumab, isatuximab);
- Participants who are refractory to the last line of therapy;

- Participants who are triple-class refractory (refractory to at least 1 IMiD, 1 PI and 1 anti-CD38);
- Participants who are penta-drug exposed (have received at least 2 IMiDs, 2 PIs and 1 anti-CD38);
- Participants who are penta-drug refractory (refractory to 2 IMiDs, 2 PIs and 1 anti-CD38);
- Participants with prior stem cell transplant and type (autologous, allogeneic or syngeneic).

Prior anticancer drug therapy will be summarized as follows based on the number and percentage of participants:

- Number of prior anticancer therapy lines: descriptive statistics, as well as broken down in categories by the number of prior lines;
- Best overall response on the last prior line of anticancer therapy received;
- Reason for stopping the last prior line of anticancer therapy.

The prior anticancer drugs will be coded in the WHO Drug coding dictionary and will be summarized based on the number and percentage of participants by preferred term. A participant will be counted only once within a given preferred term, even if he or she received the same medication at different times. The summary will be sorted in descending order in Part 1 and Part 2 combined. In case of equal frequency, alphabetical order will be used.

6.7.2. Study Conduct and Participant Disposition

6.7.2.1. Disposition

The percentages below will be calculated based on the number of participants in the Safety Analysis Set and summarized as follows:

- Number of participants enrolled and treated by country and site;
- Number and percentage of participants in each of the analysis sets defined in [Section 4](#);
- Number and percentage of enrolled participants with study intervention ongoing, discontinued or not given;
- Number and percentage of enrolled participants who discontinued the study intervention, overall and by the main reason for discontinuation of study intervention;
- Number and percentage of participants who entered follow-up;

- Number and percentage of participants who discontinued follow-up, overall and by the main reason for discontinuation of follow-up.

In addition, dispositions related to COVID-19 may be presented in a separate listing if there is significant impact of COVID-19.

6.7.2.2. Protocol Deviations

Potentially important protocol deviations will be compiled prior to database lock and will be summarized by category (n[%]) for the Safety Analysis Set.

In addition, protocol deviations related to COVID-19 may be presented in a separate listing if there is significant impact of COVID-19.

6.7.3. Study Intervention Exposure

Exposure will be summarized based on the Safety Analysis Set.

Elranatamab is administered as a subcutaneous injection. For both Part 1 and Part 2, 2 step-up priming doses regimen will be used during the first cycle as following:

- **C1D1:** Premedication + elranatamab 4 mg;
- **C1D4:** Premedication + elranatamab 20 mg;
- **C1D8:** Premedication + elranatamab 76 mg;
- **C1D15 and C1D22:** elranatamab 76 mg QW.

Starting from Cycle 2, the following dosing regimens will be assessed:

- **Part 1** will evaluate full elranatamab doses at 76 mg QW from Cycle 2 to Cycle 6. Starting from Cycle 7, the dose interval will be changed from QW to Q2W in participants with IMWG response of PR or better persisting for ≥ 2 month on QW. **Once the RP2D is identified in Part 2A**, the dose interval would also be the elranatamab RP2D (116 mg or 152 mg) Q4W in participants with IMWG response of PR or better persisting for ≥ 2 months on QW or Q2W.
- **Part 2A** will evaluate full elranatamab doses at 116 mg Q2W (**Dose level 1**) and 152 mg Q2W (**Dose level 2**) from Cycle 2 to Cycle 6. Starting from Cycle 7, the dose interval will be changed from Q2W to Q4W in participants with IMWG response of PR or better persisting for ≥ 2 month on Q2W.
- **Part 2B** will evaluate the potential RP2D from Part 2A (**Dose level 1** or **Dose level 2**) from Cycle 2 to Cycle 6 at Q2W dosing interval. Starting from Cycle 7, the dose interval will be changed from Q2W to Q4W in participants with IMWG response of PR or better persisting for ≥ 2 month on Q2W.

- CCI

For both Part 1 and Part 2, if, after switching to a less frequent dosing interval, the participant subsequently begins to have an increase of disease burden not yet qualifying as PD according to IMWG criteria, dose intervals should return to the previous dose interval for the remainder of the study.

The summary of treatment exposure to elranatamab will include the following information:

- Treatment duration (weeks);
- Number of cycles started per participant (mean, median, min, max);
- Number and percent of participants starting a cycle (any cycle, cycle 1, 2, 3, 4, 5, 6, 7, 8, 9, 10, 11, ≥ 12 cycles);
- Total cumulative dose (mg);
- Overall dose intensity (mg/week);
- Overall relative dose (%);
- Overall relative dose intensity (%);
- Number and percent of responding participants after 6 cycles who switched from QW to Q2W or Q4W (Part 1) or from Q2W to Q4W (Part 2);
- Number and percent of participants, among those switching from QW to Q2W/Q4W (Part 1) or from Q2W to Q4W (Part 2), who switched back to QW/Q2W (Part 1) or Q2W (Part 2).

The treatment duration of elranatamab (in weeks) during the study for a participant is defined as:

$$\text{Treatment duration (weeks)} = (\text{last dose date} - \text{first dose date} + 1)/7$$

The total cumulative dose (mg) of elranatamab is the sum of the actual doses that the participant received during the study; the cumulative dose (mg) of elranatamab per cycle is the sum of the actual doses that the participant received within that cycle (ie, total dose administered [mg]).

Planned treatment duration and intended treatment duration is needed to calculate dose intensity (DI) and relative dose intensity (RDI). It is defined as follows:

- Planned treatment duration (weeks) = (number of cycles started x 4) - (number of weeks in the last cycle after permanent treatment discontinuation or data cutoff for those on-treatment).
- Intended treatment duration (weeks) = (last zero/non-zero dose date – first dose date)/7 + 1 if on QW or 2 if on Q2W, or 4 if Q4W.

Note: If C1D4 is the last visit and dose is given at this visit, duration is 1 week.

The planned dose for a given cycle is defined as

- Cycle 1: Planned dose (mg/cycle) = $4 + 20 + 76 \times 3$.
- After Cycle 1:
 - If the participant is on QW dosing schedule for the cycle:
Planned dose (mg/cycle) = Full dose \times 4
 - If the participant is on Q2W dosing schedule for the cycle:
Planned dose (mg/cycle) = Full dose \times 2
 - If the participant is on Q4W dosing schedule for the cycle:
Planned dose (mg/cycle) = Full dose.

Note: For the last cycle, subtract planned doses after a participant permanently discontinues treatment or data cutoff for those on-treatment. The total planned dose is the sum of the total planned dose across all cycles.

Total planned dose is the sum of the total planned dose across all cycles.

The DI, relative dose (RD), and the RDI will be calculated for each participant across all cycles and also for each individual cycle.

- Overall DI (mg/week) = Total cumulative dose (mg)/Intended treatment duration (weeks);
- Overall Planned DI (mg/week) = Total planned dose (mg)/Planned treatment duration (weeks);
- Cycle DI (mg/week) = Cumulative dose for a given cycle (mg)/Actual cycle duration (weeks);

- Cycle Planned DI (mg/week) = Total planned dose for a given cycle (mg)/4 weeks.

The RD and RDI are defined as follows:

- Cycle RD (%) = [Total given dose for a given cycle (mg) /Total planned dose for a given cycle (mg)] × 100;
- Overall RD (%) = [Total cumulative dose (mg) /Total planned dose (mg)] × 100;
- Cycle RDI (%) = [Cycle DI (mg/week) /Cycle Planned DI (mg/week)] × 100;
- Overall RDI (%) = [Overall DI (mg/week) /Overall Planned DI (mg/week)] × 100.

Cycle DI and Cycle RDI will be summarized and plotted vs time (weeks).

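### Overall relative dose intensity is biased below 100% when data cutoff (or, depending on how it is dated, discontinuation) falls before the end of the last dosing interval

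*SAP*

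**What the plan says.** SAP 6.7.3 lists Overall RDI among the exposure outputs and defines it as "Overall RDI (%) = [Overall DI (mg/week) /Overall Planned DI (mg/week)] × 100". The two rates use different durations.

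- Overall DI is cumulative dose over Intended duration. Intended duration runs in weeks from the first dose to the last zero or non-zero dose and then adds "1 if on QW or 2 if on Q2W, or 4 if Q4W".
- Overall Planned DI is total planned dose over Planned duration. Planned duration is four weeks per cycle started, less the "number of weeks in the last cycle after permanent treatment discontinuation or data cutoff for those on-treatment".

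The dose total is trimmed by a separate note: "For the last cycle, subtract planned doses after a participant permanently discontinues treatment or data cutoff for those on-treatment". Only doses scheduled after the stop are removed, so the last dose given stays whole in both totals.

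A further note sets the duration to 1 week when C1D4 is the last visit and a dose is given, without saying which of the two durations it governs. The section does not say which date counts as permanent discontinuation.

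**The concern.** A relative dose intensity should be 100% when every dose is given in full and on time. Here the numerator rate credits time after the stop that the denominator rate leaves out, so a mid-interval cutoff lowers the ratio without any missed, delayed or reduced dose. Overall relative dose (RD) for the same participant is 100%, so two adherence measures in one table would disagree for a reason unrelated to adherence. At stake is the accuracy of a listed descriptive output in a study that evaluates longer dosing intervals.

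**Working it through.** The SAP gives no RDI value to reproduce, so the check applies its formulas to a fully compliant participant.

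**Inputs.** 28-day cycles (SAP 5.2.5). Cycle 1 dose 4 + 20 + 3 × 76 = 252 mg. For the 152 mg regimen, Cycles 2 to 6 are 2 × 152 = 304 mg each. Q4W is possible from Cycle 7: "Starting from Cycle 7, the dose interval will be changed from Q2W to Q4W" for responders in Part 2, with a corresponding rule for Part 1. Assumptions: all doses on nominal days, and the stop day itself counted as on treatment.

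**Reduction.** With full compliance, cumulative dose equals planned dose and the doses cancel:

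Overall RDI = Planned duration / Intended duration.

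If k is the interval in weeks and e the weeks elapsed from the last dose, counting its day, the shortfall is (k − e) / Intended duration. It is zero when e = k and largest when e = 1/7.

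**One case in full: 152 mg Q4W, cutoff C9D5.**
- Dose: 252 + 5 × 304 + 3 × 152 = 2228 mg, given and planned. RD = 100%.
- Intended duration: 224/7 + 4 = 36.0 weeks. DI = 2228/36.0 = 61.9 mg/week.
- Planned duration: 36 − 23/7 = 32.71 weeks. Planned DI = 2228/32.71 = 68.1 mg/week.
- RDI = 32.71/36.0 = 90.9%.

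**Cycle 7, by schedule.** At C7D1, Planned duration is 28 − 27/7 = 24.14 weeks.

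| Schedule | Intended duration at C7D1 (weeks) | RDI at C7D1 | Mean RDI over the 28 possible cutoff days |
|---|---|---|---|
| QW | 25 | 96.6% | 98.4% |
| Q2W | 26 | 92.9% | 96.6% |
| Q4W | 28 | 86.2% | 93.1% |

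If the dosing day is not counted, the Q4W value at C7D1 is 24/28 = 85.7%.

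**Q4W by stop day in Cycle 7.** D7 89.3%, D14 92.9%, D21 96.4%, D28 100%.

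**Q4W with longer treatment.** Cutoff on Day 1: 87.9% in Cycle 8, 92.0% in Cycle 12, 96.0% in Cycle 24. Mean over the cycle: 94.0%, 96.0% and 98.0%.

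**Very early stops.** Q2W at C2D1: 4.14/6 = 69.0%. QW at C2D1: 4.14/5 = 82.9%. C1D8: 1.14/2 = 57.1%.

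**Cycle RDI.** SAP 5.2.5 sets the last cycle's actual duration to the planned 28 days, and Cycle Planned DI divides by 4 weeks. A compliant last cycle therefore gives 100% whatever the cutoff day.

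**The case against.** Two stronger readings are tempting, and the documents support neither.

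The first is that any fully compliant participant scores below 100%. A stop on the last day of an interval gives exactly 100% on every schedule. For participants who discontinue, the result depends on the undefined date: dated at the last dose, the shortfall is at its largest; dated at the end of the interval, it disappears. Only the data-cutoff case is certain from the text.

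The second is that the formula by itself makes Q4W look less well delivered than QW. SAP 5.2 displays results by part, responders in both parts can move to Q4W, and no QW-versus-Q4W comparison of RDI is planned. Time on treatment drives the shortfall as much as the interval does: the early QW and Q2W stops above fall below the lowest Q4W value. Even on a single cutoff day the ordering can vanish. At C7D15, Q2W and Q4W both give 26.14/28 = 93.4%.

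It is also fair to say that 86.2% is a corner case requiring cutoff on the day of the first Q4W dose, and that many participants on Q4W at a cutoff will be well past Cycle 7. That stands, with one limit. SAP 6 triggers the full analysis after 6 months of response follow-up, which at 30.4375 days per month is 182.6 days, about C7D15. Participants with the shortest follow-up who are still on treatment will be in the cycle where a Q4W shortfall is largest.

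Finally, unaffected measures are already planned: Overall RD, Cycle RDI (summarised and plotted over time), and the interruption and delay tables in SAP 6.7.3.1. They limit the harm but do not make Overall RDI right.

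**Conclusion.** The definition is wrong as written, for a descriptive output. Overall RDI is biased downward for participants whose cutoff falls before the end of the last interval, and for those who discontinue if the undefined date falls there too. The size is at most just under 1, 2 or 4 weeks divided by Intended duration. In the cycles where Q4W is possible, that means several percentage points for Q4W and one to two for QW on average in Cycle 7, shrinking afterwards; very early stops lose much more on any schedule. These figures assume nominal dosing days and, for the averages, a cutoff equally likely on each day of the cycle. Nothing in the primary endpoint, the DLT rate, the futility rule or the efficacy analyses depends on it.

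**What to change.** End both durations in SAP 6.7.3 by the same rule. Define Planned duration as

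4 × (cycles started − 1) + nominal weeks from Day 1 of the last cycle to the last planned dose on or before discontinuation or cutoff + the interval in force (1, 2 or 4 weeks).

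For the C9D5 case this gives 4 × 8 + 0 + 4 = 36 weeks, equal to Intended duration, so RDI is 100%. Keeping the nominal cycles-started basis matters, because real delays must still lower RDI. If Cycle 9 had started one week late, Intended duration would be 231/7 + 4 = 37 weeks and RDI 36/37 = 97.3%.

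Also:
- apply the C1D4 note to both durations;
- state which date counts as permanent discontinuation;
- add a programming check that full compliance gives 100% under QW, Q2W and Q4W for every stop day.

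The cost is one replaced formula, two clarifying sentences and one check. No new data are needed, and dosing and total planned dose do not change.

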6.7.3.1. Dose Reductions, Interruptions, and Delays

Dose Reduction

A dose reduction is defined as a non-zero dose that is less than the prior dose and less than the planned dose in the protocol.

The number and percentage of participants with at least 1 dose reduction as well as a breakdown of dose reductions (1/2/3/ ≥4) will be summarized. In addition, the number and percentage of participants with at least 1 dose reduction due to AE will also be summarized.

Dose Interruption

An interruption is defined as missing a scheduled dose based on the planned dosing frequency (QW, Q2W or Q4W).

The number and percentage of participants with dose interruptions as well as a breakdown of dose interruptions (1/2/3/ ≥4) will be summarized. In addition, the number and percentage of participants with at least 1 dose interruption due to AE will also be summarized. Percentages will be calculated based on the total number of participants in the Safety Analysis Set.

Dose Delay

A dose delay will be derived based on study drug administration date and will be grouped into the following categories based on the deviation of the actual to the planned treatment administration day (relative to the previous treatment administration date):

- No delay;
- 1-3 days delay;
- 4-6 days delay;
- 7 or more days delay (only in the Q2W and Q4W schedule).

The number and percentage of participants with delayed study drug administration and maximum length of delay, ie, the worst case of delay if participants have multiple dose delays will be summarized by cohort, as applicable.

6.7.4. Concomitant Medications and Nondrug Treatments

The following analyses will be based on the Safety Analysis Set.

Concomitant medications are medications, other than study medications, which started prior to first dose date of study intervention and continued on during the on-treatment period as well as those started during the on-treatment period. **Prior medications** are medications, other than study medications, which are started before the first dose of study intervention.

Prior and concomitant medications will be summarized from the ‘Prior and Concomitant Medications’ eCRF page. Pre-medications required for CRS will also be summarized separately from the ‘Pre-Medication Treatment’ eCRF page.

Summary of prior medications, concomitant medications (excluding for CRS prophylaxis) and summary of pre-medications will include the number and percentage of participants by ATC Classification Level 2 and preferred term. A participant will be counted only once within a given drug class and within a given drug name, even if he or she received the same medication at different times. If any prior or concomitant medication is classified into multiple ATC classes, the medication will be summarized separately under each of these ATC classes. The summary tables will be sorted in descending frequency of ATC class and descending frequency of drug name in a given ATC class in Part 1 and Part 2 combined. In case of equal frequency regarding ATC class (respectively drug name), alphabetical order will be used. Medications without an ATC classification Level 2 coded term will be summarized under the ‘Unavailable ATC classification’ category.

Summary of prior and concomitant medications for CRS prophylaxis will include the number and percentage of participants by preferred term only.

6.7.5. Subsequent Anticancer Therapies

The following analyses will be based on the Safety Analysis Set.

Number and percentage of participants with any anticancer therapy after discontinuation of study intervention will be tabulated overall and by type of therapy based on the data collected from the ‘Next Anticancer Therapy (NXT CNCR)’ eCRF pages, ‘Non-drug Treatments (NXT RAD)’, ‘Non-drug Treatments (NXT SURG)’, and ‘Transplant details (TRANSPLT)’ eCRF pages.

Subsequent anticancer drug treatment will be summarized by preferred term.

6.8. Safety Summaries and Analyses

The Safety Analysis Set will be the primary population for safety evaluations. Summaries of AEs and other safety parameters will be based on the Safety Analysis Set.

6.8.1. Adverse Events

All analyses will be based on treatment emergent adverse events (TEAE) unless otherwise specified. Treatment emergent is defined in [Section 3.5](#). AEs not considered treatment emergent will be flagged in data listings. Summaries of TEAEs due to COVID-19 may be produced if appropriate.

A high-level summary of adverse events (all causality and treatment-related, separately) will include the number and percent of participants with:

- Any TEAEs;
- Serious TEAEs;
- Grade 3-4 TEAEs ;
- Grade 5 TEAEs;
- TEAEs leading to dose interruptions;
- TEAEs leading to dose reductions;
- TEAEs leading to dose interruptions or reductions;
- TEAEs leading to permanent discontinuation of study intervention;
- CRS;
- ICANS;
- Peripheral neuropathy.

Seriousness, toxicity grade, and withdrawal from drug are as reported by the investigator on the adverse event CRF.

An event will be considered treatment related if the investigator considered the event related to the study drug, or if relationship is missing.

For all the AE summaries by SOC and PT, or PT only, the following cytopenias will be clustered. Each participant will be counted only once within each SOC and clustered terms. However, the number of total events will be based on the individual PTs.

- Thrombocytopenia (PT=Thrombocytopenia; Platelet count decreased);
- Anaemia (PT=Anaemia; Haemoglobin decreased, Red blood cell count decreased, Haematocrit decreased, Normochromic anaemia, Normocytic anaemia, Normochromic normocytic anaemia);

- Neutropenia (PT=Neutropenia; Neutrophil count decreased, Neutrophil percentage decreased, Cyclic neutropenia, Agranulocytosis, Granulocytopenia, Granulocyte count decreased);
- Leukopenia (PT=Leukopenia; White blood cell count decreased);
- Lymphopenia (PT=Lymphopenia and PT=Lymphocyte count decreased, Lymphocyte percentage decreased, CD4 lymphocytes decreased, CD4 lymphocyte percentage decreased, CD8 lymphocytes decreased, CD8 lymphocyte percentage decreased).

Summaries by SOC and PT (by alphabetical order for SOC and by descending order of frequency for PT in Part 1 and Part 2 combined) will be provided for:

- Any TEAEs (all causality and treatment-related);
- TEAEs by maximum toxicity grade (all causality and treatment-related);
- TEAEs with Grade 3-4 (all causality and treatment-related);
- TEAEs leading to death (all causality and treatment-related);
- TEAEs leading to dose interruptions (all causality);
- TEAEs leading to dose reductions (all causality);
- TEAEs leading to dose interruptions or reductions (all causality); TEAEs leading to permanent discontinuation of study intervention (all causality and treatment-related);
- Serious TEAEs (all causality and treatment-related).

Each participant will be counted only once within each SOC and PT.

The following summaries will be provided by PT only (by descending order of frequency in Part 1 and Part 2 combined) for:

- Most common TEAEs by PT and maximum severity grade (all causality and treatment-related, separately);
- Most common serious TEAEs by PT and maximum severity grade (all causality).

Each participant will be counted only once within each PT.

In case a participant has events with missing and non-missing toxicity grades, the maximum of the non-missing grade will be displayed. Missing grade will only be displayed in the event that only 1 event has been reported for a participant and the grade is missing.

